## 1. BACKGROUND

The human genome has evolved around periods of restricted food intake and is highly adapted with the relevant pathways to cope with this. Yet, there are still gaps in our understanding of these physiological responses. In the absence of energy intake, the body

maintains life by using stored energy, which is sufficient to sustain life over a prolonged period (> 1 year) if energy stores are sufficient [1]. In particular, the shift in metabolic substrate initially acts to maintain glucose before then acting to try and spare muscle tissue. However, there is also a significant shift in amino acid metabolism, and little research has explored this in human skeletal muscle and or adipose tissue. Furthermore, to the best of our knowledge, little or no research has investigated changes in the genes/proteins that regulate lipid/glucose metabolism in adipose tissue in response to prolonged fasting.

Furthermore, it has been established that periods of prolonged fasting result in a reduction in skeletal muscle insulin sensitivity [2], perhaps due to the excess of fatty acids resultant from severe energy deficit. However, this has primarily been established using proof of principle methods (e.g. oral, or intravenous tolerance tests). Whilst these have been invaluable in establishing effects, it is also important to employ more ecologically valid models, such as mixed meal tolerance tests.

## 2. OVERVIEW OF PROPOSED RESEARCH

### 2.1 Hypothesis

Due to the exploratory/novel nature of the model this is not considered hypothesis driven research.

### 2.2 Aims and Objectives

#### Aims

1. To establish the metabolic/molecular response in both adipose tissue and skeletal muscle to acute starvation (~82 h).
2. To establish the sensory experience to prolonged fasting (pain, fatigue, drive).

#### Objectives

Assess Amino acids in adipose, skeletal muscle and circulation in response to prolonged fasting

Assess postprandial response to a meal pre and post prolonged fast

Assess anthropometric changes in response to prolonged fasting

Assess the sensory experience in response to prolonged fasting

[figure not shown]
### 2.3 Rationale

We plan to study participants before, after and during ~82 hours of no energy intake. Whilst few studies have extended starvation beyond 48-72 h, this duration is sufficient to observe the established shift towards greater reliance on lipids to fuel metabolism [2-5]. Necessarily, extension of the starvation beyond this duration therefore guarantees stability in the reliance on endogenous fuels (e.g. NEFAs, and ketones). At the level of the adipose tissue, an increase in the efflux of NEFA from adipose tissue as well as a reduction in glucose uptake is apparent during the early stages of a prolonged fast (~20 h) [5-7]. Necessarily, given that changes in metabolism within the adipose tissue occur this rapidly, it is surprising that so few studies have included measures of this tissue under conditions of prolonged fasting. In particular, assessment of genes and proteins responsible for regulating substrate metabolism in the adipose tissue would provide interesting insight into the metabolic flexibility of this tissue under severe energy deficit. Furthermore, measurement of amino acids and their respective ketoacids in adipose, skeletal muscle, and the circulation would further our understanding of how these metabolically important tissues respond in order to preserve/maintain skeletal muscle during energy deficit [2, 8].

Surprisingly, only one study to date has investigated changes in post-prandial metabolism following mixed meal ingestion, as opposed to oral or intravenous tolerance tests [2, 9, 10]. Notably, whilst this study aimed to achieve a 72-h starve, provision of the mixed meal tolerance test immediately prior to beginning the 72-h starvation period resulted in an actual starve duration closer to ~2 days. Given the dramatic effect of acute starvation on gastric emptying [9] it is especially important to investigate the meal responses. Furthermore, given that insulin resistance following prolonged fasting persists even following a 24 h refeed, it would be insightful to include measures of sequential meals (i.e. the response to the standardised lunch and dinner will be assessed via continual glucose monitors). Finally, few, if any, studies have assessed the physical activity response to periods of prolonged fasting. Necessarily, methods such as doubly labelled water would not be appropriate due to the underlying assumptions with RQ as well as only giving a total energy expenditure value. Alternatively, employment of combined heart rate/accelerometry (Actiheart), would be appropriate in order to assess the change in physical activity levels, whilst giving a detailed breakdown in changes in intensity.

**2.4 Study design**

This study will employ a single-arm, non-randomised design in which participants will act as their own control prior to undergoing 3 days of starvation. The control phase includes ~3 days of habitual energy balance assessment before coming into the laboratory for baseline metabolic and anthropometric assessment. Participants will be provided with monitoring equipment throughout the 3 days of starvation and will be asked to provide a blood sample as well as record their blood pressure, weight, and urinary ketones each day. On the middle day participants will also be asked to come into the lab to provide a blood sample at 2000 h.

**Figure 1.** Protocol schematic depicting the study design.

## **2.5 Outcome measures**

### *Primary*

Metabolic response to feeding before and after a prolonged fast  
Change in amino acid metabolism (i.e. BCAAs and ketoacids) in skeletal muscle, adipose tissue, and in the circulation

### *Secondary*

Change in circulating glycerol and FFAs across the prolonged fast (indices of lipolysis from adipose tissue)

Change in Autophagy (in skeletal muscle and neutrophils)

Total nitrogen (or at least urea nitrogen) in urine (24h collection) throughout the fast (or at least 1st vs last day)

Change in plasma lactate and pyruvate in response to prolonged fasting (indices of Cori cycle)

Change in urinary (acetoacetate), and circulating (beta-hydroxybutyrate) ketones in response to prolonged fasting.

Change in body mass, pre-post, and during the prolonged fast.

Change in blood pressure pre-post, and during the prolonged fast.

Change in waist-hip circumferences pre-post the prolonged fast.

Change in sensory experience (pain, fatigue, drive) in response to prolonged fasting.

Change in haematocrit/haemoglobin pre-post the prolonged fast.

Change in grip strength pre-post the prolonged fast.

Change in reaction time pre-post the prolonged fast.

Change in aspects of immune function and infection risk

Change in interstitial fluid glucose concentrations pre-, post-, and during the prolonged fast (assessed via continual glucose monitoring)

Occurrence of adverse events (e.g. nausea, vomiting, migraines)

## **2.6 Statistical analysis**

### *Sample estimate:*

Due to the drastic nature of the intervention outlined (i.e. the complete abstinence from energy intake), a relatively small sample size will be required. As such, based on previous research, a sample size of 6-10 participants should be sufficient to observe changes in metabolism with this duration of fast.

Descriptive statistics will be calculated using Microsoft Excel. Normality of data will be assessed using GraphPad Prism 8.0. Repeated measures ANOVA Will be employed to identify significant effects of TREATMENT & TIME for post-prandial data. Paired t-test or Wilcoxon will be used to compare variables assessed only pre-and post-intervention. One-way ANOVA will be used to assess changes in variables assessed each day. Bonferroni post-hoc tests will locate significant differences where they exist. Normalised confidence intervals will be calculated to plot as error bars on figures. The magnitude of these CIs directly infers the difference between means at each time point (i.e. statistical significance) rather than variance of individual values around the mean.

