### 4. Trial days

3 days prior to the first experimental visit participants will visit the laboratory to be fitted with a continual glucose monitor, an actiheart activity monitor, as well as a food diary and food scales. They will be asked to record energy intake and to standardise physical activity, caffeine, and alcohol intake.

Upon finishing the 3 days of lifestyle standardisation participants will enter the laboratory for where weight, height, waist:hip circumference, sagittal-abdominal diameter, and skin-fold will be assessed prior to assessment of resting metabolic rate, blood pressure and urinary ketones. Participants will also undergo grip strength, reaction time, and sensory experience assessment. Following this, samples of skeletal muscle and adipose tissue will be collected from the *vastus lateralis* and abdominal adipose tissue respectively. An intravenous cannula will then be placed a 10 mL blood samples will be drawn before ingestion of a carbohydrate rich porridge breakfast (7.3 mg carbohydrate·kJ).

A 3-hour postprandial period follows the ingestion of breakfast with blood samples will be collected at 15, 30- and 60-minute intervals during the first, second and third hour respectively alongside hourly expired gas samples and assessment of subjective appetite and mood. Upon completion of the 3-hour post-breakfast period, participants will have completed the visit and will be provided with a standardised lunch and dinner. Participants will also be provided with urinary ketone sticks, a blood pressure monitor, a set of weighing scales, as well as an actiheart monitor.

Participants will be asked to assess urinary ketones using provided assessment sticks in the evening at 2000 h.

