### 5. Intervention

Participants will be provided with their last meal at ~1900 h on the day of the meal testing. From this point onwards, participants will be asked to refrain from eating for ~82 hours until their return visit to the laboratory. Throughout this period of extended fasting participants will be provided with 80 mmol sodium and 40mmol potassium daily (to consume in the form of slow-release tablets) to minimize the confounding effects of fluid deprivation and intravascular volume depletion on cardiovascular reflexes and sympathetic nervous system activity. Subjects will also be permitted to consume water, non-sugared carbonated drinks

and, with the exception of the day of the pre/post measurements, non-sugared decaffeinated coffee and tea (if they normally consume tea and coffee).

Upon waking each day participants will be asked to assess their urinary ketone levels, blood pressure, and weight. Participants will be asked to repeat this in the evening at 2000 h.

Each day participants will be asked to return to the laboratory to provide a blood sample. On the second day of starvation participants will also be asked to provide a blood sample at 2000 h.

Furthermore, throughout the intervention participants will be asked to wear an actiheart monitor in order to assess physical activity levels in response to prolonged fasting.

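### Does leaving the choice between paired t-test and Wilcoxon open undermine a sample of 6 to 10?

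*Combined protocol and SAP*

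**What the plan says.** Section 2.6 is the whole statistical plan. On size it says "a sample size of 6-10 participants should be sufficient to observe changes in metabolism with this duration of fast", resting on earlier research that it does not quantify. On tests it says "Paired t-test or Wilcoxon will be used to compare variables assessed only pre-and post-intervention", and two sentences before that, "Normality of data will be assessed using GraphPad Prism 8.0". Post-prandial data go to repeated measures ANOVA and daily measurements to one-way ANOVA. For the figures it plans normalised confidence intervals and adds: "The magnitude of these CIs directly infers the difference between means at each time point (i.e. statistical significance").

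The pre/post-only group includes part of a primary outcome. Section 2.5 lists "Change in amino acid metabolism (i.e. BCAAs and ketoacids) in skeletal muscle, adipose tissue, and in the circulation". At the baseline visit "samples of skeletal muscle and adipose tissue will be collected" (section 4), and section 6 repeats that visit after the fast, so tissue values come in pairs. Blood is different: "Each day participants will be asked to return to the laboratory to provide a blood sample" (section 5), so circulating amino acids can be analysed as a daily series.

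Section 7 provides no follow-up testing for people who stop after one day, but asks those who stop after two days to attend it. Section 2.1 sets the frame: "Due to the exploratory/novel nature of the model this is not considered hypothesis driven research".

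**The concern.** Section 2.6 gives no alpha, sidedness, named normality test or threshold, and no explicit link between the normality check and the test used. Nor does it say whether 6 to 10 counts people enrolled or people with both biopsies.

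At this size the choice of test can matter. A signed-rank test on very few pairs has a coarse p-value scale. If 6 people enrol and one stops after the first day, 5 pairs remain, and an exact two-sided test cannot then reach 0.05 however large the effect. Two things would be at stake. An analyst could pick the test after seeing the data. And a non-significant tissue result that could never have been significant might be read as no change, in participants who had been biopsied twice.

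**Working it through.** **Inputs.** From the plan: 6 to 10 participants, the two named tests, the normality check, biopsies at two visits, and the stopping arrangements. The plan's 6 to 10 cannot be reproduced, because it gives no effect size, SD, power, alpha or dropout rate. Assumed: two-sided 0.05; exact signed-rank test with no zero changes; loss of a pair in 5, 10 or 20% of participants; a standardised mean change of 1.44 for illustration; and Shapiro-Wilk at 0.05 on the changes as the normality check.

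**1. The Wilcoxon floor.** The smallest two-sided p with n pairs is 2/2^n.
- n = 5: 2/32 = 0.0625, so 0.05 is out of reach.
- n = 6: 2/64 = 0.03125 if all six changes agree in direction; the next value is 4/64 = 0.0625.
- n = 10: significant as long as the ranks of the opposite changes sum to 8 or less (p = 0.0488).

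The floor depends on the assumptions. At n = 5 a one-sided exact test reaches 1/32 = 0.031, and the normal approximation without continuity correction gives 0.043.

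**2. The other named test.** The paired t-test has no floor. For 80% power it needs a standardised change of about 1.68 at 5 pairs, 1.43 at 6 and 1.00 at 10. With normal changes, exact Wilcoxon power at 6 pairs is Φ(d)^6: at d = 1.44, 0.9251^6 = 0.627; it reaches 80% at d = 1.79.

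**3. Chance of 5 or fewer pairs.** With N enrolled and loss q, this is P(X ≤ 5) for X ~ Binomial(N, 1 − q). For N = 6 it is 1 − (1 − q)^6.

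| N enrolled | q = 5% | q = 10% | q = 20% |
|---|---|---|---|
| 6 | 26.5% | 46.9% | 73.8% |
| 8 | 0.6% | 3.8% | 20.3% |
| 10 | 0.01% | 0.16% | 3.28% |

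**4. Chance that such a comparison also goes to Wilcoxon.** In simulation the normality check chose Wilcoxon in 5 to 17% of 5-pair samples, depending on the distribution. Applying that rate to every shortfall, as an approximation:
- N = 6: from 0.265 × 0.05 = 1.3% to 0.738 × 0.17 = 12.5%.
- N = 8: at most 0.203 × 0.17 = 3.5%.
- N = 10: at most 0.0328 × 0.17 = 0.56%.

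**5. Would another rule do better?** Simulated power, normality check versus paired t-test throughout:
- 5 pairs: 64–65% v 67–68% (normal concentrations); 34–60% v 36–63% (log-normal).
- 6 pairs: 79–80% v 80–81% (normal); 64–77% v 52–77% (log-normal).

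So the check costs 2 to 4 points at 5 pairs and at most about 1 point at 6, where it can also gain. A t-test on logs at 6 pairs gives 80–81% if concentrations are log-normal but 67–79% if they are normal. Type I error at 5 pairs is 4–5% for both the t-test and the check with symmetric changes, and 8–12% v 8–11% with skewed ones. No rule is clearly better.

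**6. Figure intervals.** If the normalisation is within participant with the two-condition correction (assumed), √2 times the plotted half-width equals the paired-t half-width, so the figure gives the paired-t decision. A figure that shows a difference where the exact Wilcoxon cannot arises in 2 to 4% of 5-pair samples.

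**The case for a change.** The strongest case for acting is that the answer turns on choices the plan leaves unstated. For a standardised change of 2.0 at 5 pairs, power is about 90% by paired t-test and 0% by exact Wilcoxon, and nothing in writing stops an analyst from deciding late. The exploratory label does not fully excuse this, since the plan names primary outcomes and speaks of significant effects. A few sentences would cost almost nothing.

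Part of this stands. The omissions are real, and a non-significant result on 5 or 6 pairs says little about absence of change. But the 90 v 0 contrast sets the t-test against Wilcoxon used throughout. That is an unlikely reading of a section that names the t-test first and assesses normality. The rule one would naturally write down is the one already implied. It too selects the test from the data, and it still sends some 5-pair samples to Wilcoxon. Defining the range as completed pairs would go beyond wording: it could mean one more person undergoing biopsies at two visits.

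**Conclusion.** The concern is right in its arithmetic but does not call for a change. What is missing is detail that an analyst would fill sensibly: assess normality of the changes, use the paired t-test unless it fails, state the level and sidedness, and give the number of pairs and the estimated change with its interval in the report.

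The floor bites only if several unstated conditions coincide: enrolment at or near the low end, at least one lost pair, a failed normality check, and an exact two-sided test at 0.05. Under assumed losses of 5 to 20% that is about 1.3 to 12.5% of tissue comparisons with 6 enrolled, at most 3.5% with 8 and under 0.6% with 10. It touches the muscle and adipose part of one primary outcome and the other variables measured only before and after. It does not touch the meal response or the daily blood series. Spelling out the implied rule would not alter power or type I error, and the alternatives examined give no consistent gain. For a study that disclaims hypothesis testing, the remaining caution concerns how a non-significant result is read.

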## **6. Follow up visit**

Upon completion of the intervention, participants will visit the laboratory at the University of Bath, and repeat the pre-intervention visit with the porridge breakfast. Following this repeated visit, participants will again be provided with a standardised lunch and dinner.

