## **7. Ethical considerations of risk and discomfort**

Acute starvation may cause discomfort for participants including headaches and lack of energy. All participants will be supervised by a member of the research team throughout the protocol. Participants who drop out after one day of fasting will not be included in follow up testing, but will be provided with food to break their fast. Conversely, participants who decide to not continue with study following 2 days of fasting will be asked to come in for follow up testing/standardised meal provision. Biopsies also introduce a risk for discomfort for participants but will only be performed by trained and experienced members of staff who follow the guidelines for safe practice. Intravenous cannulation has the potential to cause minor discomfort and bruising. Furthermore, there is a small associated risk of infection and/or embolism, where blood flow to the vein becomes partially restricted. In order to minimise these risks, cannulation will only be carried out by qualified and experienced staff members. The cannula is an essential aspect will only be in the vein for a maximum of 3 hours per laboratory visit, whereas the venepuncture needle on days 1,2, and 3 of the fast will be removed as soon as the sample is obtained.

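### The post-prandial repeated measures ANOVA has no rule for incomplete profiles, and conventionally one missing blood value of 16 removes a participant from that analyte's analysis

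*Combined protocol and SAP*

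**What the plan says.** Section 2.6 (Statistical analysis) names one method for the meal-test data, with TREATMENT and TIME as the effects to be tested: "Repeated measures ANOVA Will be employed". These data serve a primary outcome in section 2.5, "Metabolic response to feeding before and after a prolonged fast". On numbers, section 2.6 says "a sample size of 6-10 participants should be sufficient to observe changes in metabolism with this duration of fast".

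Section 4 (Trial days) has a pre-meal draw ("blood samples will be drawn before ingestion of a carbohydrate rich porridge breakfast") and then a three-hour schedule: "blood samples will be collected at 15, 30- and 60-minute intervals during the first, second and third hour respectively". Under section 6, participants return after the fast and "repeat the pre-intervention visit with the porridge breakfast".

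Nothing covers a missed draw, a spoiled sample or a failed assay. There is no mixed model, imputation or interpolation rule, analysis population or replacement of participants. Section 7 foresees early stopping ("Participants who drop out after one day of fasting will not be included in follow up testing"; those who stop after two days are asked to attend), but it settles only who is tested, not how incomplete data are analysed.

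**The concern.** A two-factor within-subject ANOVA, computed in the usual way, works on a full participant by visit by time table. If a cell is empty, either the participant is dropped for that analyte or the analyst makes an unplanned repair after seeing the data. Dropping discards up to 15 valid values because one is missing. With 6 to 10 participants, losing one is 17% of the sample at the low end (1/6) and 10% at the high end (1/10). An unplanned repair leaves a choice open on a primary outcome.

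**Working it through.** **Plan's own figure.** The range of 6 to 10 cannot be reproduced, because the documents give no alpha, power, effect size or SD. The effect sizes, loss rates and two-sided 0.05 below are therefore assumptions.

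**Values per participant and analyte** (sections 4 and 6)
- Before the meal: 1.
- After the meal: 60/15 + 60/30 + 60/60 = 4 + 2 + 1 = 7.
- Per visit: 8. Over two visits: 16.

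**Chance of a complete profile.** If each sample is lost independently with probability p, P(complete) = (1 − p)^16.

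| p | P(complete) | Expected complete of 6 | Expected complete of 10 | P(at least one lost), n = 6 | P(at least one lost), n = 10 |
|---|---|---|---|---|---|
| 1% | 0.851 | 5.1 | 8.5 | 62% | 80% |
| 2% | 0.724 | 4.3 | 7.2 | 86% | 96% |
| 5% | 0.440 | 2.6 | 4.4 | 99% | over 99% |

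**Power.** The TREATMENT main effect is equivalent to a paired t-test on visit means. Its power comes from the noncentral t with noncentrality d√k, where d is the mean difference divided by the SD of the paired differences and k is the number of complete participants. I averaged this over the binomial distribution of k, counting k below 2 as zero power. Example for n = 6, d = 1.5, p = 2%, taking k = 6, 5, 4, 3, 2 in turn:

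0.144 × 0.833 + 0.329 × 0.711 + 0.314 × 0.533 + 0.160 × 0.316 + 0.046 × 0.133 = 0.58.

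| n | d | No loss | 1% | 2% |
|---|---|---|---|---|
| 6 | 1.5 | 83% | 71% | 58% |
| 6 | 2.0 | 97% | 88% | 76% |
| 10 | 1.0 | 80% | 71% | 61% |
| 10 | 2.0 | 100% | 99.6% | about 97% |

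These figures cover the TREATMENT main effect only, not the visit-by-time interaction.

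**Is the loss recoverable?** A simulation (2,000 runs; assumed SDs: participant 1, participant-by-visit 0.5, residual 0.5; samples missing at random) compared complete-case analysis with a time-adjusted paired analysis of all available samples, as a stand-in for a mixed model.
- n = 6, d = 1.5: 69% against 84% at 1% loss, and 57% against 81% at 2% (82% with nothing missing).
- n = 10, d = 1.0: 72% against 81% at 1%, and 62% against 81% at 2% (80% with nothing missing).

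Using all observed samples recovers nearly all of the power. Differences of a point or two are simulation error.

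**Which mixed model?** The ANOVA tests TIME against participant-by-time variation. A model with only participant and participant-by-visit random effects pools that variation into the residual. I simulated complete data under the null (4,000 runs; assumed SDs: participant 1, participant-by-visit 0.5, participant-by-time 0.5, residual 0.7). At n = 6 and n = 10 that shorter model rejected TIME about 15% of the time and visit by time about 0.5%. The ANOVA rejected each about 5% of the time. The participant-by-time term is therefore needed.

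**The case against.** A reader might infer that the plan prescribes deletion. It does not. It never uses the words balanced, classical or listwise, and it names neither a fitting method nor ANOVA software (GraphPad Prism 8.0 is mentioned only for normality). Deletion follows from the conventional method when no other rule is given; it is not a stated intention.

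A reader might also infer that one failed sample costs the participant's whole meal-test record. The loss is per analyte: a failed assay for one leaves the others intact. The count of 16 does not carry over to the hourly gas, appetite and mood data. The muscle and adipose amino acid measures, also primary, are outside the point.

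The size is open to challenge as well. Draws come from a cannula placed by experienced staff, so losses may be rare. They may also cluster when a cannula fails, and then fewer people are hit. If losses come in runs averaging 3 samples (an assumption), P(complete) is roughly (1 − p)^(16/3), about 95% at p = 1% and 90% at p = 2%, against 85% and 72% under independence. The plan also argues that the intervention is drastic. At n = 10 with an effect of 2 SD, power stays at about 97% with 2% loss, so a general claim that the study cannot afford the loss is not supported. At n = 6 and 2 SD, however, power falls from 97% to 76% at the same loss rate.

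It is also tempting to say that draws fail more often after the fast and so bias the comparison. That is possible, but nothing in the documents shows it.

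Section 2.1 says that the research is not hypothesis-driven, which softens the weight of power figures. It does not remove the need for a rule, because section 2.6 plans significance tests on these data.

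**Conclusion.** The point stands as a gap in the analysis plan: a primary outcome is to be analysed by a method that conventionally needs all 16 blood values per analyte, and nothing says what happens when one is missing. At assumed independent losses of 1% to 2%, about 0.9 to 1.7 of 6 participants, or 1.5 to 2.8 of 10, would be expected to drop out of an analyte's analysis. The power cost is roughly 13 to 25 points at n = 6 with a 1.5 SD effect and 9 to 19 points at n = 10 with a 1.0 SD effect. It is less with clustered losses and small at n = 10 with effects near 2 SD. The count of 16 and the absence of a rule come from the documents; the loss rates, their independence, the effect sizes and alpha do not. A better method is available at little cost, so the wording should be amended. The documents do not support a claim that the study fails without the change.

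**What to change.** In section 2.6, replace the post-prandial ANOVA with a linear mixed model fitted by REML to all observed samples:
- fixed effects: visit (the plan's TREATMENT), time, and visit by time;
- random effects: participant, participant-by-visit and participant-by-time;
- Kenward-Roger or Satterthwaite degrees of freedom;
- a sensitivity analysis allowing serial correlation between samples within a visit.

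With complete data and non-negative variance estimates, this reproduces the two-way repeated measures ANOVA tests. State that no participant is excluded for isolated missing samples, and report the number of missing values by analyte and visit.

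The model cannot supply a within-person contrast for a participant who stops after one day and has no second meal test (8 of 16 values absent). Report those participants separately.

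The cost is a wording change and slightly more programming; visits, sampling and sample size stay as they are. The downsides are a missing-at-random assumption and the risk of zero variance estimates or convergence problems with 6 to 10 participants. The plan should therefore say in advance what will be done if the model does not converge.

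### For blood analytes, the planned ANOVA TREATMENT effect weights unevenly spaced draws equally, so it depends partly on the draw schedule and moves when only curve timing changes

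*Combined protocol and SAP*

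**What the plan says.** Section 2.5 lists as its first primary outcome "Metabolic response to feeding before and after a prolonged fast". It does not say which feature of the response is meant (average level, area, peak or time course).

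Section 2.6 gives the analysis: "Repeated measures ANOVA Will be employed to identify significant effects of TREATMENT & TIME for post-prandial data". It adds Bonferroni post-hoc tests and confidence intervals plotted at each time point. It names no area under the curve, incremental area, time-weighted mean, peak or time to peak, and no TREATMENT x TIME interaction.

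Section 4 (Trial days) fixes the sampling. Before the meal, "blood samples will be drawn before ingestion of a carbohydrate rich porridge breakfast". Then "A 3-hour postprandial period follows the ingestion of breakfast", during which "blood samples will be collected at 15, 30- and 60-minute intervals during the first, second and third hour respectively". The other post-meal measures are hourly: "alongside hourly expired gas samples and assessment of subjective appetite and mood".

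Section 2.3 gives a reason to expect a change in timing: "Given the dramatic effect of acute starvation on gastric emptying [9] it is especially important to investigate the meal responses".

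**The concern.** In a balanced repeated measures ANOVA, the TREATMENT main effect compares the two visits on the plain average of all samples. When draws crowd into the first hour, that average leans towards the first hour. It is then not the average response over the three hours, but an average whose weights were set by the phlebotomy schedule.

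This does little harm if the curve keeps its timing. Here the protocol itself cites an effect of starvation on gastric emptying, which can move the curve in time. With front-loaded weights, a curve that moves later looks smaller and one that moves earlier looks larger, even at the same 0-180 min exposure. A real rise in exposure in a delayed curve can also be hidden. At stake is the only single-number before-after contrast that the plan offers for blood analytes in the first-listed primary outcome, in a study of 6-10 people.

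**Working it through.** **Inputs from the documents.** Draw times (section 4): one pre-meal sample (0), then 15, 30, 45, 60, 90, 120 and 180 min. That is 8 samples, of which 7 are post-meal. The period is 180 min. The plan states no figure for weights, curve shape, SD or effect size, so there is nothing of its own to reproduce here.

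**1. What the main effect averages.** With k samples per visit, each carries weight 1/k. As a check on simulated data (8 participants, 8 times), the ANOVA TREATMENT F(1,7) was 46.51, and the squared paired t on each participant's unweighted mean was also 46.51.

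**2. Weights.** The trapezoid weight of a draw is half the sum of its two neighbouring intervals, divided by 180. At 120 min, for example, it is (30 + 60)/2/180 = 0.250.

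| min | 0 | 15 | 30 | 45 | 60 | 90 | 120 | 180 |
|---|---|---|---|---|---|---|---|---|
| ANOVA | 0.125 | 0.125 | 0.125 | 0.125 | 0.125 | 0.125 | 0.125 | 0.125 |
| Trapezoid | 0.042 | 0.083 | 0.083 | 0.083 | 0.125 | 0.167 | 0.250 | 0.167 |

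- 0-60 min samples, pre-meal sample in the model: 5/8 = 62.5%, against 41.7% by trapezoid.
- Post-meal samples only: 4/7 = 57.1%, against 36.4% by trapezoid over 15-180 min.

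**3. Simple check.** Take two identical triangles with peak 3 units, one over 0-60 min and one over 60-120 min. The trapezoid mean is 0.500 for both. The 8-sample plain means are 0.750 and 0.375, a two-fold difference from timing alone.

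**4. Smooth illustration (assumed shape).** Excursion above the pre-meal level: E(t) = A(t/p)exp(1 - t/p), with peak A at time p. Before the fast, A = 3 and p = 30.

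The exact area over 0-180 min is A·e·p·[1 - exp(-180/p)(1 + 180/p)]. For p = 30 this is 3 × 80.13 = 240.4. After the fast, A is chosen to give the same area. For p = 60, A = 240.4/130.6 = 1.84.

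- Before, at the eight draws: 0, 2.47, 3.00, 2.73, 2.21, 1.22, 0.60, 0.12; plain mean 1.543.
- After, p = 60: 0, 0.97, 1.52, 1.77, 1.84, 1.68, 1.35, 0.75; plain mean 1.235.
- Change: 1.235/1.543 - 1 = -20.0%, or -0.31 units.

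| Post-fast peak (min) | Plain mean | Trapezoid mean | True rise in 0-180 area that gives zero plain-mean difference |
|---|---|---|---|
| 20 | +11.3% | -2.3% | not applicable |
| 45 | -12.8% | +0.1% | 14.7% |
| 60 | -20.0% | -0.3% | 25.0% |
| 75 | -24.1% | -0.6% | 31.7% |

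The last column is 1/(1 + change) - 1; for a 60-min peak, 1/0.800 - 1 = 25.0%. The percentages are the same with seven samples, because the excursion is zero at time 0.

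**5. Same curves, equal total area.** Suppose instead that the whole response is only delayed, so that A·p is constant (A = 2.0, 1.5, 1.2 for p = 45, 60, 75). Part of the curve then falls after 180 min. The trapezoid mean changes by -7%, -19% and -30%, and the plain mean by -19%, -35% and -47%.

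**6. Rejection rates (assumed noise).** Paired test, peak 30 to 60 min, equal 0-180 min area, n = 6, 8, 10.

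- Amplitude CV 0.2, sample SD 0.3, visit SD 0.2: the plain mean rejects 23%, 32% and 40% of the time.
- CV 0.3, SDs 0.4 and 0.3: 13%, 17% and 21%.
- Trapezoid mean: about 5% throughout. With equal total area instead, it rejects 11-32% of the time.

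**The case against.** The strongest reply is that the documents never make the 0-180 min average the target. Section 2.1 says that the research is not hypothesis driven. Section 2.6 reads as a time-course analysis, with TIME effects, post-hoc tests and intervals at each time point. On that reading, a moved curve is a real change in the response to feeding, and detecting it is no error. This stands in part. It rules out one tempting inference, that the 13-40% in step 6 is an inflated type I error rate. Those rates apply only to a null of equal 0-180 min area, which the plan does not state, and they rest on assumed curves and SDs.

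Three further limits stand.

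- A reader might infer that the first hour supplies 62.5% of the response. The figure is a share of sample weight, and it needs the pre-meal sample in the model, which the plan leaves open. The like-for-like comparator is about 42%, not the one-third of clock time.
- A reader might infer that the trapezoid mean removes the effect of timing. Its near-zero change in step 4 follows largely from fixing the 0-180 min area. Step 5 shows that it still falls when the response runs past 180 min, though by less than the plain mean in each of those cases.
- Section 2.3 gives neither the direction nor the size of the change in gastric emptying, and a one-peak curve need not suit every analyte.

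A TREATMENT x TIME interaction, if fitted, could flag a timing shift. It would not correct the main effect, and the plan does not name it.

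**Conclusion.** The point holds for blood analytes. As written, the TREATMENT main effect is an unweighted mean over unevenly spaced draws, with 62.5% of the weight (57% without the pre-meal sample) on the 0-60 min samples, against about 42% under trapezoid weights over 0-180 min. These weights follow from the schedule and need no assumption beyond a balanced ANOVA.

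The consequence is conditional. If curve timing changes, the main effect moves even at unchanged 0-180 min exposure: by -13% to -24% of the mean excursion for peaks moved from 30 to 45-75 min, under an assumed curve. The documents give no curve, peak time or SD, so these are illustrations and not predictions. They do not show that the trial's result will be wrong, or that any stated error rate is breached. Expired gas, appetite and mood are hourly and evenly spaced, so the point does not reach them.

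The change is worth making because it is cheap and the outcome is primary. It is an improvement to the definition of the summary and does not bear on the validity of the design.

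**What to change.** In section 2.6, state that the size of the post-prandial response for each blood analyte is the time-weighted mean: trapezoidal area over 0-180 min divided by 180, from actual draw times, for each participant and visit. Compare it before and after the fast with the paired t-test or Wilcoxon test already planned, in place of the ANOVA TREATMENT main effect. Keep the repeated measures ANOVA for TIME, TREATMENT x TIME (to be named) and the time-point comparisons, so that changes in timing are reported separately from changes in size. State whether the pre-meal sample enters the ANOVA.

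The cost is one or two sentences and a short calculation on samples already taken. There are two downsides. The 120-min sample rises from 12.5% to 25% of the weight and the 180-min sample from 12.5% to 16.7%, so an error in either counts for more. The summary also covers only three hours, so a delayed response that continues past 180 min will still look smaller (-7% to -30% in step 5, against -19% to -47% for the plain mean). The report should say so.
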